#### **4.5.5. Other Research Assessments**

Structured patient interviews will be conducted within two weeks before completing the Week 24 visit for a subset of English language-speaking patients (up to 50 patients) enrolled at US centers. The interview will be conducted by phone and will collect information in the patient's words regarding their perceptions of functionality and ALS symptom burden, activities of daily living, and experiences in the trial.

Hospitalizations experienced by a patient following randomization will be determined by the Investigator as being either related to ALS, unrelated to ALS, or indeterminate. Hospitalizations deemed related to ALS cover those that are related to disease progression, hospitalizations that may occur to address an ongoing ALS symptom or to be preventative (such as hospitalization for a PEG / RIG tube), as well as those to address a complication of a treatment being received for ALS. This information will be recorded and entered into the EDC. Hospitalizations that are for social reasons, or those that were planned prior to the patient signing the ICF are not considered SAEs and therefore relationship to ALS will not be recorded.

Biomarkers are objective measures or indicators of normal biological processes, pathological processes or pharmacological responses to a therapeutic intervention. Biomarker development may be useful to identify disease subtypes, guide therapy, detect a response to therapy, better understand the development of an adverse event, or predict disease severity. Where authorized by the applicable IRB/EC/REB approved informed consent, blood samples for biomarker development will be collected pre-AM dose on Day 1 and Week 24. Plasma samples will be stored for future biomarker analyses.

Where authorized by the applicable IRB/EC/REB approved informed consent and authorized by the patient, a blood sample will be obtained at the Day 1 visit and stored for possible future genetic testing related to this study and for research purposes only.

## 5. PLANNED ANALYSES

### 5.1. Interim Analyses

Two interim analyses are planned for this trial. The interim analysis methods and the specifications of the data snapshots will be detailed in an interim analysis plan.

Twelve (12) weeks after approximately one-third or more of the planned sample size is randomized, the first interim analysis may be triggered. Its purpose is to determine if there is a lack of effect of reldesemtiv on the ALSFRS-R in CY 5031, a finding that would be inconsistent with the prior observed effect on the change from baseline at 12 weeks in ALSFRS-R total score in the Phase 2 trial, CY 5022. At this interim analysis, the Data Monitoring Committee (DMC) will receive unblinded efficacy data from the independent, third-party biostatistical group supporting them and assess the effect of reldesemtiv on the change from baseline to Week 12 in the ALSFRS-R total score. At this interim assessment, if the treatment difference for change from baseline to Week 12 in ALSFRS-R total score has a one-sided p-value larger than or equal to 0.5 (ie, the estimated treatment difference of the change from baseline at Week 12 in ALSFRS-R total score is favoring placebo), the DMC may recommend stopping the trial due to futility. This futility analysis based on the data of change from baseline to Week 12 in ALSFRS-R will not have any alpha spending. The Sponsor will monitor the blinded aggregate standard deviation of the change from baseline to Week 12 in ALSFRS-R total score periodically and possibly adjust the specified alpha before this interim analysis is conducted.

Twenty-four (24) weeks after at least one-third of the planned sample size is randomized; the second interim analysis will be triggered. The safety analysis will include all data points collected from available patients at the time of the interim data review. The efficacy analysis will include patients who would be expected to complete 24 weeks of the study by the time of data cut off for the second interim data review, i.e., those who complete 24 weeks of the study and those who are expected to complete 24 weeks of the study but early terminate prior to Week 24. Those patients who have not had the opportunity to reach Week 24 by the time of the data cutoff will not be included in the second interim efficacy analysis. The goal of the second interim analysis is to evaluate whether the proposed Phase 3 trial has adequate power to achieve a statistically significant effect on the primary endpoint in the final primary analysis, given the planned enrollment, or if continuing the trial is futile. At this interim analysis, the DMC will receive unblinded efficacy data from the independent, third-party biostatistical group supporting them and assess the effect of reldesemtiv on the primary endpoint. In terms of futility, the DMC may recommend stopping the trial if the conditional power (CP) under the current trend is less than 0.10 for the primary endpoint. The futility boundary is non-binding. The DMC is to make a recommendation to stop the trial using their collective judgment and the totality of evidence available. The DMC may consider the first secondary endpoint in a similar fashion.

If the CP of primary endpoint is within a pre-specified promising zone from 0.40 to 0.90, the DMC may recommend increasing the sample size by a pre-specified fixed number of 150 unless there is any safety concern or other concerns that preclude the recommendation. This method is referred to as the CDL adaptive method and was initially proposed by Chen, DeMets, and Lan, later extended by Gao, Ware and Mehta, and Mehta and Pocock ([Chen 2004](#); [Gao 2008](#); [Mehta 2011](#), respectively). It is used to control type-1 error for sample size increase based on unblinded interim data. Within the pre-specified promising zone and a pre-specified fixed increase of the

sample size, the CDL method could allow the final analysis to include all data before and after the interim look without inflating the type-1 error. This interim analysis will spend a very small 2-sided alpha of 0.0001 for the primary endpoint as well as all individual secondary endpoints. The DMC is also expected to recommend stopping this trial due to superiority if a two-sided p-value is  $\leq$  alpha of 0.0001 for the primary endpoint as well as all individual secondary endpoints. Therefore, the significance level of 2-sided alpha of 0.0499 would be used for the final analyses for the primary endpoint and all individual secondary endpoints to control familywise error rate at overall alpha of 0.05.

## 5.2. Final Analyses

When all patients complete or discontinue from the study, the final analyses will be conducted.

If the interim analysis result leads to an increase of the sample size, the final primary analyses will be further stratified by the status of being included or excluded from the 2nd interim analysis. As a sensitivity analysis, the adjusted point estimation and confidence interval after the adaption ([Lawrence 2003](#)) will also be provided. For the joint rank test on the first secondary endpoint, the ranking will be made separately for the cohort that is included in the 2nd interim analysis and for the subsequent cohort that is not included in order to maintain independence of the results for the cohort included in the interim analysis and the subsequent cohort that is not eligible for inclusion in the interim analysis.

## **6. GENERAL CONSIDERATIONS FOR DATA ANALYSES AND HANDLING**

### **6.1. General Summary Table and Individual Subject Data Listing Considerations**

Unless otherwise specified, analyses will be conducted for the first 24-week double blind placebo-controlled period and the second 24-week active drug period.

Efficacy data will be summarized by randomized treatment group based on the full analysis set (FAS). Safety data will be summarized by treatment received based on the safety analysis set, and PK data will be summarized for patients who receive reldesemtiv based on the pharmacokinetics analysis set.

Descriptive statistics to be presented in a table include count of patients, mean, median, standard deviation, minimum and maximum for continuous variables, and count of patients and the percentage for categorical variables.

For model based analysis, least squares mean, difference of least squares means between treatment groups and the corresponding standard errors, 95% confidence intervals (CIs) and two-sided p-values for the relative statistical inferences will be presented.

For survival analyses, time to event will be summarized by median, 95% CI of median, and 1st and 3rd quartiles using Kaplan-Meier technique. Counts and percentages of events and censored will be presented. Hazard ratio between treatment groups and the corresponding 95% CI and p-value will also be presented.

Listings will include patient ID, demographics, randomized treatment group and other relevant items, and sorted by randomized treatment group, patient ID and date of assessment.

### **6.2. General Post Text Summary Table and Individual Subject Data Listing Format Considerations**

Post text tables and individual subject data listings are prepared according to ICH Guideline E3.

### **6.3. Data Management**

Data will be entered into the clinical database with programmed edit checks and direct visual inspection to ensure integrity. Adverse events, concomitant medications and medical history will be coded programmatically while unique terms will be reviewed visually. Clinical safety laboratory, ECG and PK data and FVC measurements collected from a spirometry at remote visits will be provided in the pre-specified format from external laboratories or research organizations. ALSAQ-40 data collected on CRF and from spirometry will be combined for analysis. Every attempt will be made to obtain measurements to minimize the percentage of missing data.

Critical data will be identified at an early stage of the study to allow sufficient time to have data entered, reviewed, queried and cleaned throughout the study. In preparation for the interim data snapshot, clean CRFs will be soft-locked, which will prevent sites from modifying data on those CRFs.

The final analyses will include data included in the interim analyses, plus additional data that are collected after the interim analyses. The data that are soft locked for the interim analyses will not be modified for the final analyses unless permission is granted from Cytokinetics that a site needs to change the data based on the SOPs. The data management group may break a soft lock to issue a query as needed. Changes for log records such as AE end dates may be updated as appropriate.

## **6.4. Data Presentation Conventions**

The following conventions will be applied to data presentations:

- For continuous variables, mean and median values are formatted to one more decimal place than the measured value. Standard deviation values are formatted to two more decimal places than the measured value. Minimum and maximum values are presented with the same number of decimal places as the measured value.
- For categorical variables, the count and percentage of responses are presented in the form XX (XX.X%).
- Date variables are formatted as DDMMYYYY for presentation. Time is formatted from 0:00 to 23:59 as HH:MM for presentation.
- P-values, if applicable, will be presented to 4 decimal places. If the p-value is less than 0.0001 then it will be presented as <0.0001. If the rounded result is a value of 1.000, it will be displayed as >0.9999.
- Unless otherwise stated, any statistical tests performed following the second interim analysis (which will be performed at a significance level of 0.0001) will use 2-sided tests at the 0.0499 significance level.

The table and listing shells and table of contents as part of this SAP provide the expected layout and titles of the tables, listings and figures. Any changes to format, layout, titles, numbering, or any other minor deviation will not necessitate a revision to the SAP nor will it be considered a deviation from planned analyses. Only differences in the analysis methods or data handling will require such documentation. The appropriate listings supporting the tables will be included and are not specified in the individual sections throughout the document.

## **6.5. Analysis Populations**

### **6.5.1. Screen Failures**

Screen Failures include patients who sign the informed consent form but are not eligible for study enrollment; therefore, they were not dispensed study drug. Screen failures will not be included in the efficacy and/or safety analyses. However, reasons for screen failures will be summarized. For patients who failed at the first screening and were rescreened, the eligibility at the rescreening visit will be used to determine if the patients are screen failures.

### **6.5.2. All Randomized Set**

All Randomized Set includes patients who are randomized to receive reldesemtiv or placebo.

### **6.5.3. Safety Analysis Set**

Safety analysis set will include all randomized patients who receive any amount of study drug. Patients will be analyzed according to the actual treatment received during the double-blind placebo-controlled period.

### **6.5.4. Full Analysis Set**

Full Analysis Set (FAS) consists of randomized patients who receive any amount of study drug and have a baseline and at least 1 post baseline efficacy assessment or have survival status recorded during the double-blind placebo-controlled period. Patients will be analyzed according to the treatment to which they are assigned at randomization.

### **6.5.5. Pharmacokinetic Analysis Set**

Pharmacokinetic Analysis Set includes all patients who have at least one measurable plasma concentration of reldesemtiv, provided that they have no major protocol violations or deviations that could affect the PK of reldesemtiv.

## **6.6. Baseline Definition**

Unless otherwise specified, baseline is defined as the last available measurement taken prior to administration of the first dose of study drug.

## **6.7. Derived and Transformed Data**

### **6.7.1. Baseline Age**

Age at screening will be collected on the eCRF and used as the baseline age and for all data derivations involving age regardless of age changes during the study.

### **6.7.2. Study Day**

If the date of interest occurs on or after the first dose date, then study day will be calculated as (date of interest – date of first dose) + 1. If the date of interest occurs prior to the first dose date, then study day will be calculated as (date of interest – date of first dose). There is no study day 0.

### **6.7.3. Change from Baseline**

Change from baseline is calculated as (post baseline result – baseline result).

Percent change from baseline is calculated as (change from baseline / baseline result) x 100%.

If either the baseline or the post-baseline result is missing, the change from baseline and/or percentage change from baseline will be set to missing.

### **6.7.4. Analysis Windows**

Since study visits do not always take place exactly as scheduled per protocol, it is necessary to assign the actual observation dates to analysis windows for analysis purposes.

For measurement taken prior to the first dose of study drug, the analysis window is defined as the interval of time prior to the first dose of study drug. Measurements taken on or after the first dose of study drug will be assigned to the next scheduled analysis window.

For data collected at a scheduled post baseline visit, the analysis window will be assigned based on the scheduled study day of the nominal visit as collected on the eCRF.

For unscheduled post baseline visits, early discontinuation visit or follow-up visit, measurements taken on or after the first dose of study drug will be assigned to an analysis window using defined lower and upper bounds for each analysis window. Measurements assigned in an analysis window will have study day greater than or equal to the lower bound but no greater than the upper bound of the analysis window. The lower bound and the upper bound for the analysis windows are defined as the midpoints of the scheduled visits for all assessments (see [Section 12.3](#)).

Visits are identified as the nominal visits according to the eCRFs. Each visit will be identified with the visit descriptor (eg, "Week 24"). If a patient has two or more study visits in one analysis window, one record will be flagged as the "analyzed record" for that analysis window.

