2.3. Benefit/Risk Assessment

2.3.1. Risk Assessment

In CY 5022, treatment emergent adverse events (TEAEs) reported more frequently for the reldesemtiv groups than for the placebo group (with a difference in patient incidence of $> 5\%$) were cystatin C increased, GFR decreased, and fatigue. TEAEs that appeared to increase in frequency with increasing dose included fatigue, nausea, cystatin C increased, GFR decreased, alanine aminotransferase (ALT) increased, and aspartate aminotransferase (AST) increased.

Serum cystatin C was obtained in CY 5022 and used to determine the estimated glomerular filtration rate ($eGFR_{CysC}$) as it was previously recognized that exposure to reldesemtiv resulted in a rise in creatinine; this was attributed to Organic Cation Transporter 2 (OCT2) inhibition. There was a dose dependent decline in $eGFR_{CysC}$ from baseline in CY 5022 and therefore the rise in creatinine observed in prior studies could not be ascribed solely to OCT2 inhibition. Mean $eGFR$ declined to an essentially stable level by 2 weeks of active treatment and tended to recover after 4 weeks off drug. Decline in $eGFR_{CysC}$ was the most common reason for early termination of study drug due to AEs, occurring in 7/457 (1.5%) participants. No patients had significant sequelae related to the decline in $eGFR_{CysC}$ such as requiring dialysis or developing hyperkalemia.

Elevations in ALT or AST greater than $3 \times$ upper limit of normal (ULN) occurred in 25 patients; 24 (7.0%) were assigned reldesemtiv and 1 (0.9%) assigned placebo. Overall, the transaminase elevations appeared to be transient, dose dependent, mild to moderate, and not associated with increase in bilirubin or any clinical manifestations.

A total of 6 patients (none of whom had concurrent elevations in ALT or AST $> 5 \times \text{ULN}$), all on reldesemtiv and 5 in the 450 mg bid group, had a postbaseline total bilirubin value $> 2 \times \text{ULN}$. All elevations were observed within approximately 1 month of starting reldesemtiv dosing and resolved or were normalizing at last contact.

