- End of Week 2: remote visit (lab only)
- End of Week 4: clinic visit/lab
- End of Week 8: remote visit/lab
- End of Week 12: clinic visit/lab
- End of Week 16: remote visit/lab
- End of Week 20: remote visit/lab
- End of Week 24 (last dose of double-blind dosing): clinic visit/lab
- End of Week 26: remote (lab only)
- End of Week 28: remote visit/lab
- End of Week 32: remote visit/lab
- End of Week 36: clinic visit/lab
- End of Week 40: remote visit/lab
- End of Week 44: remote visit/lab
- End of Week 48 (last dose of active drug dosing): clinic visit/lab
- Follow-Up (4 weeks after last dose of study drug): clinic visit/lab

For patients who complete Week 48 and want to enter the open label extension (OLE), they will not have the follow-up visit; instead they will enter the OLE on the same day as their Week 48 visit. If the patient does not want to enter the OLE, or if the OLE has not yet been approved at the site, the follow-up visit will take place as above.

Remote Visits

Remote visits are defined as any of the following contacts with the patient: home (or other location outside of the clinic) phlebotomy draw, telephone calls, telemedicine, and video contact. Patients will be provided a device to enable telemedicine contact for the remote visits. Screening and Day 1 visits must occur in-clinic; in addition, it is strongly encouraged that Week 24 and Week 48 visits take place in the clinic. Week 48 must take place in clinic if the patient is enrolling in the OLE study at the Week 48 visit. In-clinic visits can be converted to remote visits in the event the clinic is closed to patient care, or if the investigator believes the health of the patient would be best served by replacing the in-clinic visit with a remote one. The medical monitor must be contacted in advance of converting an in-clinic visit to a remote visit.

Standard of Care for ALS

[figure not shown]
Since we plan to conduct the trial in different regions of the world, including Europe, Canada, Australia and the US, standard of care regarding ALS for the local region as determined by the physician in discussion with the patient should be followed. Standard of care may include, but is not limited to, therapies for the treatment of ALS that have been approved in the respective regions where the trial is conducted.

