7.2.1. Management of Patients after Permanent Discontinuation of Study Drug

If study drug is permanently discontinued, the patient should be encouraged to remain in the trial to continue to obtain outcome measures and safety data.

There are several options for a patient after permanently discontinuing study drug:

- Patient agrees to continue to return to clinic for all remaining in-clinic study visits and agrees to all planned remote visits.
- Patient only agrees to complete the early discontinuation (ED) visit as soon as possible after the decision is made, the follow-up visit 4 weeks after the last dose taken, and additional follow-up visits dependent upon lab results; it is preferred these are done in clinic but can be done remotely if that is not feasible.

- Patient only agrees to complete the ED visit; it is preferred this is done in clinic but can be done remotely if that is not feasible.
- Patient only agrees to remote visits to obtain patient study data. Patients should be strongly encouraged to come into the clinic for Week 24.
- Patient agrees to a mix of remote and in-clinic visits to obtain study data. Patients should be strongly encouraged to come into the clinic for Week 24.
- Patient only agrees to allowing contact for determination of vital status at Week 24 and Week 48
- Patient withdraws consent (see [Section 7.6](#)) and does not agree to any further study procedures or visits.

Assessments obtained at the early discontinuation and subsequent follow-up visit are listed in the Schedule of Activities. Details of the assessments to be performed at the additional visits following drug discontinuation, should the patient agree to be followed via either in-clinic or remote visits, can be found in the Study Manual.

Patients that have not withdrawn consent and have difficulty returning for all remaining study visits can be contacted by phone or video call to obtain patient study data.

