#### **6.7.5. Multiple Assessments**

Once analysis windows are assigned, a patient's individual analysis window could potentially contain more than one visit. Records from all visits, including scheduled, unscheduled and early discontinuation visits could be flagged as the "analyzed record" within the analysis window, although the records from scheduled visit will take priority.

For measurement taken prior to the first dose of study drug, in the event of multiple visits falling within an analysis window, the following rule will be used to determine the "analyzed record":

- The record closest to, but prior to the first dose of study drug should be selected as the baseline "analyzed record." This could include scheduled visits and other screening visits.

For post baseline visits, measurements taken during the 24-week double-blind, placebo-controlled period will be included only in the analysis windows up to Week 24. Measurements taken after patients transition to the active drug period will be included only in the analysis windows after Week 24. Once patients transition to the active drug period, all measurements collected on or after the transition date will not be included in the analysis windows for the first 24 weeks double-blind placebo-controlled period. Furthermore, in the event of multiple visits falling within an analysis window, the following rules will be used in sequence to determine the "analyzed record" for the analysis window:

- If a scheduled visit occurred during the analysis window, then the measurement taken from the scheduled visit will be used.
- If no scheduled visit occurred during the analysis window, the measurement taken closest to the scheduled day will be used as the "analyzed record."
- If no scheduled visit occurred during the analysis window and there is a tie between unscheduled visits in the number of days before and after the scheduled day, measurements from the later visit will be used as the "analyzed record."

For all analyses, only the “analyzed record” within each analysis window will be summarized in a table. If there are other visit records within the analysis window, they will only be included in data listings. In addition, composite scores (eg, ALSFRS-R total score or muscle strength mega score) will be calculated based on the “analyzed record.”

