**Table 15: Analysis Windows for Clinical Safety Laboratory Measurements**

Visit	Scheduled Day	Lower Bound	Upper Bound
Screening	<1	<1	<1
Day 1	1	1	1
Week 2	15	2	21
Week 4	29	22	42
Week 8	57	43	70
Week 12	85	71	98
Week 16	113	99	126
Week 20	141	127	154
Week 24	169	155	175
Week 26	183	176	189
Week 28	197	190	210
Week 32	225	211	238
Week 36	253	239	266
Week 40	281	267	294
Week 44	309	295	322
Week 48	337	323	350
Follow-up	365	351	>351

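### SAP 6.7.4 files the follow-up visit by study day rather than by time since last dose, so most early stoppers' off-drug safety values fall under treatment-week labels and out of the Follow-up row

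*SAP*

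**What the plan says.** **How the follow-up visit is windowed.** SAP 6.7.4 treats three kinds of record together: "For unscheduled post baseline visits, early discontinuation visit or follow-up visit, measurements taken on or after the first dose of study drug". These "will be assigned to an analysis window using defined lower and upper bounds for each analysis window". SAP 6.7.2 fixes the clock at first dose: on or after that date, "study day will be calculated as (date of interest – date of first dose) + 1". In SAP 12.3, Tables 9, 10, 11, 13 and 15 (the last titled "Analysis Windows for Clinical Safety Laboratory Measurements") give Follow-up a scheduled day of 365 and a lower bound of 351. None refers to last dose.

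**When the visit takes place.** For a patient who stops drug early, Protocol 7.2.1 describes "the follow-up visit 4 weeks after the last dose taken". Completers who enter the open-label extension have no such visit: "they will not have the follow-up visit; instead they will enter the OLE on the same day as their Week 48 visit" (Protocol 4.1).

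**Which record is tabulated.** Under SAP 6.7.5 a scheduled visit in the window takes priority. Without one, the record nearest the scheduled day is used, and a tie between unscheduled visits goes to the later one.

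**Drug status.** SAP 9.5 to 9.7 summarise laboratory values, vital signs and ECG by time point with no on-drug cut-off. The only exclusion of data after drug discontinuation is in the exploratory delayed-start comparisons (SAP 8.8.2).

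**The concern.** The follow-up visit is the one visit defined by time off drug. The protocol uses it to check whether adverse events of special interest have resolved (Schedule of Activities, note 7). Part of its renal risk assessment is that mean eGFR in CY 5022 "tended to recover after 4 weeks off drug" (Protocol 2.3.1). A window keyed to first dose fits this visit only for patients who take drug to about Week 48.

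For anyone who stops earlier there are two consequences. An off-drug value can become the tabulated value for a treatment week, with nothing to mark it. And the Follow-up row loses the patients who stopped early, who are the ones whose recovery a safety reader most wants to see.

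**Working it through.** **1. Reproduce the SAP's bound.** Week 48 is scheduled on day 337 and Follow-up on day 365. Midpoint = (337 + 365) / 2 = 351, the stated lower bound. Day 365 is itself the completer's timing: 336 days of dosing + 28 = 364 days, which is study day 365. The tables are internally correct; it is the anchor that does not suit early stoppers.

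**2. Earliest last dose that reaches the Follow-up window.** Follow-up day = last-dose day d + 28. The condition d + 28 ≥ 351 gives d ≥ 323.
- Last-dose days 1 to 336: 322 of 336 (95.8%) map to a treatment-week window in Tables 9, 10, 13 and 15.
- Last-dose days 1 to 168: 168 of 168.
- Neurological examination (Table 12, Follow-up from day 267): d ≥ 239 is needed, so 238 of 336 (70.8%) map to Week 24.

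These are counts of possible last-dose days, not of patients.

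**3. Laboratory examples (Table 15).**

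| Last dose (day) | Follow-up (day) | Window | Filed as |
|---|---|---|---|
| 57 | 85 | 71–98 | Week 12 |
| 140 | 168 | 155–175 | Week 24 |
| 160 | 188 | 176–189 | Week 26 |
| 322 | 350 | 323–350 | Week 48 |
| 323 | 351 | 351 on | Follow-up |

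The day-160 patient never entered the active drug period, yet the record takes a label from it. The period rule in SAP 6.7.5 does not prevent this: day 188 is past the 24-week period, and the patient made no transition, so only the bounds decide.

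**4. ECG (Table 13, Week 24 window days 2–252).** The Schedule of Activities has an ECG at both the early-discontinuation and follow-up visits. Assume the first is on about the last-dose day d, the second on d + 28, and no Week 24 visit is attended. The follow-up ECG is nearer day 169 when |169 − (d + 28)| < |169 − d|, that is |141 − d| < |169 − d|, so d < 155. Example d = 29: distances are 169 − 29 = 140 and 169 − 57 = 112, so the off-drug ECG is tabulated and the one closer to dosing goes only to listings.

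**5. Size of the mixing.** The plan expects 444 of 555 patients to complete 24 weeks: 555 − 444 = 111. Assume that all 111 stop drug, evenly over days 1–168, and that all attend follow-up with no scheduled visit in the same window. Follow-up days then run from 29 to 196, and each window receives 111 × (days covered) / 168:

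| Lab window | Days covered | Records |
|---|---|---|
| Week 4 | 14 | 9.3 |
| Weeks 8, 12, 16, 20 | 28 each | 18.5 each |
| Week 24 | 21 | 13.9 |
| Week 26 | 14 | 9.3 |
| Week 28 | 7 | 4.6 |

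The documents do not give the number of records per window. Taking 444 to 555, the largest share is between 18.5 / 555 = 3.3% and 18.5 / 444 = 4.2%; at about 500 it is 3.7%. If recovery were complete, a mean change would shrink by roughly that share.

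**The case against.** **Recovery is measured.** A reader might infer that reversibility goes unassessed in early stoppers. The documents do not support that. Safety laboratory tests are drawn at Follow-up, with further testing if events of special interest persist. Liver tests are followed to baseline or normal (Protocol 7.4). Renal tests may be repeated 2–3 times weekly until disposition (Protocol 7.3). Laboratory values are listed for patients with events of special interest (SAP 9.2.4) and generally (SAP 9.5). What is missing is a table.

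**The windows are not called on-treatment.** A reader might also infer that the SAP presents off-drug values as on-drug. It does not: the labels are visit weeks, and patients who stop drug are encouraged to keep attending, so scheduled off-drug values enter these windows too. An unrestricted summary is a legitimate choice. What stands is that off-drug records are unflagged and that a visit defined by time off drug loses that identity.

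**The renal rule limits the number affected.** Meeting a renal threshold leads to a hold with possible restart, and patients who restart keep their scheduled visits. Carrying over the CY 5022 figure of 7/457 (1.5%) stopping for eGFR decline would be unsafe. That was a 12-week trial with a 450 mg arm, and the denominator includes placebo. No patient count is drawn from it here.

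**Most safety signals survive.** Post-baseline abnormality incidence, shift to maximum severity, multiples-of-ULN counts and time to elevation do not depend on averaging a recovered value. This stands.

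**The gap may be filled elsewhere.** Table shells are in a separate document, and SAP 6.7.5 does not name follow-up among its examples of eligible records. But 6.7.5 makes records from all visits eligible, and shells set layout (SAP 6.4), not window assignment. The silence is a further reason to state the rule.

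**Conclusion.** The point holds as a defect in a stated rule for by-visit safety summaries, and nothing else in the SAP repairs it. With follow-up at 28 days after last dose, every stop before day 323 sends that visit's laboratory, vital-sign and ECG records to a treatment-week window, where they are tabulated if no scheduled visit lies there. The Follow-up row is left to patients who take drug to day 323 or later and do not enter the extension.

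The numerical effect on by-visit means is modest. About 4% of a window is an upper limit, because the 111 can include deaths, withdrawals and patients who skip the visit, and because scheduled visits take priority. No arm-specific stopping rate at this dose is given, so the documents do not show how the dilution would differ between arms. The greater loss is the absence of any table of recovery in early stoppers.

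Efficacy is outside the point: SAP 8.6.1 uses observed data to Week 24 whatever the drug status, and off-drug ALSFRS-R values are consistent with that. The change should be made, but no efficacy conclusion depends on it.

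**What to change.** For safety variables only:

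1. **SAP 6.7.4 and 12.3:** assign the protocol follow-up visit to a category 'Follow-up (4 weeks after last dose)' whatever its study day.
2. **SAP 6.7.5:** state that a follow-up record cannot be the analyzed record for a treatment-week window.
3. **SAP 9.5 to 9.7:** flag each by-visit record as on or off drug from the recorded dose dates. This also covers patients who stop drug but keep attending.
4. **SAP 9.5:** add a by-arm summary of eGFR, UPCR and liver tests at Follow-up, as change from baseline and from the last on-drug value, with early discontinuers shown separately.

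The cost is SAP wording and a little programming; dose start and stop dates are already collected (Protocol 6.4). The downside is slightly fewer records in scheduled windows.
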